#### 4.6. Step 6 (Visits 21, 23, 24) – Immune Monitoring and Leuk #2

Following the final HXTC infusion, participants move into Step 6 for a minimum of three additional visits. The 2nd leukapheresis will occur at Visit 23 (Week 16), approximately 5 weeks after the last HXTC infusion to evaluate the effect of study treatment on the IUPM by QVOA.

All participants who receive greater than 8 doses of VOR (3200 mg) will be required to enter a study cancer registry where they will be contacted once a year for 5 years after completion of their study participation. The registry was created to monitor participants for the development of future malignancies given concern for genotoxic impact with the use of VOR.

NOTE: THE PROTOCOL AMENDMENT FOR VERSION 4.0 DATED 31 JANUARY 2022 ELIMINATED VISITS 22, 25, AND 26 FROM STEP 6 OF THE PROTOCOL.

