#### **6.1.7. Dosage, Preparation, and Administration of HXTC**

Each dose of HXTC is  $1 \times 10^8$  cells/m^2 and each participant will receive five infusions at this dose, provided there are enough manufactured T-cells. If unable to manufacture enough cells for five infusions at  $1 \times 10^8$  cells/m^2 participants will receive five infusions at a dose  $\geq 5 \times 10^7$  cells/m^2 up to  $1 \times 10^8$  cells/m^2 as determined by the protocol team.

The first HXTC infusion (HXTC #1) will be infused approximately 6 hours after the 1st dose of VOR (Step 4, Visit 7) and the 2nd HXTC infusion (HXTC #2) after the 6th dose of VOR (Visit 10) in Step 4. In Step 5 each participant will receive the next three HXTC infusions. The 3rd HXTC infusion (HXTC #3) will be infused approximately 6 hours after the 11th dose of VOR 400 mg (Step 5, Visit 14) and HXTC infusion #4 will occur approximately 6 hours after the 16th dose (Step 5, Visit 16). The 5th or last HXTC infusion (HXTC #5) occurs 1 to 3 days after the 20th dose of VOR (Visit 19).

In preparation of each HXTC dose of  $1 \times 10^8$  cells/m^2, an extra - volume (1 – 20%) is added to account for cell loss. When possible, CETI will cryopreserved the cells at  $1 \times 10^8$  T cells per mL, allowing the cells to be thawed and injected directly. However, the cell concentrations can vary from time to time; therefore, dosage calculations and body surface area (BSA) are calculated both at CETI (prior to shipment) and then by two independent licensed practitioners at the UNC site prior to administration to confirm accurate dose delivery.

The required amount of HXTCs for the infusions are shipped to the UNC HPC Lab, where they are stored and maintained in biological safety cabinets (BSC). If extra cells are produced, CETI archives these aliquots at their manufacturing site. These stored aliquots are accessible for additional infusions under IND 15984 or research analysis.

All study HXTC infusion visits occur in the UNC CTRC. After completion of all required clinical assessments prior to the infusion, the HXTC product is thawed, delivered and verified with the study coordinator. Review of the HXTC product occurs prior to administration per the UNC HIV Cure Center SOP entitled Cellular Product Infusion Guidelines and Emergency Management Plan.

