Participants are pre-medicated with cetirizine (Zyrtec) and acetaminophen (Tylenol).

- Cetirizine
  - All infusions – administer 10 mg PO
- Acetaminophen
  - All infusions – administer 500 mg PO (weight <65 kg) or 650 mg PO (weight  $\geq$ 65 kg).

Cell Administration: HXTC will be given by IV infusion at a rate of 4-6 mL/min through a peripheral line.

Post infusion monitoring lasting at least 60 minutes follows each infusion.

Participants will receive supportive care for acute toxicity directly attributable to HXTC, as appropriate.

All treatments will be given at the University of North Carolina at Chapel Hill.

The grading system for drug toxicities is located in the Division of AIDS (DAIDS) Table for Grading the Severity of Adult and Pediatric Adverse Events, Version 2.1. [July 2017], which can be found on the DAIDS RSC Web site:  
<http://rsc.tech-res.com/safetyandpharmacovigilance/>

A period of six weeks following the completion of the last infusion will constitute the time required for clinical safety monitoring and reporting of adverse events related to infusions.

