#### 9.2.3. Adverse Event Reporting Period

The AE reporting period for each participant begins when the participant signs the consent and lasts through the 30 days following the EOS visit in Step 6, Visit 24. During Step 1 and Step 3 (prior to study product administration), any AE that occurs will be collected as concurrent medical history (pre-existing condition) and not as an AE, unless it is due to a protocol-related procedure (e.g., leukapheresis or large blood collection for HXTC manufacturing).

AEs leading to discontinuation, AEs of  $\geq$  Grade 3 severity, related adverse events, and lab abnormalities as well as safety concerns will be recorded in the database as well as communicated in a timely manner to the UNC IRB, Children's National Health System IRB, NHLBI, FDA, and Merck per the reporting requirements of each regulatory entity.

The Sponsor of this study is UNC-CH. The principal investigator ([name]) at UNC-CH will be responsible for reporting to all the regulatory bodies and funding sources listed above.

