## **10. STATISTICAL CONSIDERATIONS**

### **10.1. General Design**

This is a phase I, single-site study to evaluate the effects of VOR and HXTC therapy on persistent HIV-1 Infection in HIV-infected individuals suppressed on ART. Twelve participants with durable viral suppression will be enrolled and will complete the study. All participants will receive the same treatment and if eligible, will be dosed with VOR and receive HXTC infusions. Participants will continue their baseline ART regimen throughout the study.

If the baseline IUPM  $\geq 0.3$ , participants will have a blood sample sent to CNH for production of HXTCs. Upon release of HXTC, participants will be clinically assessed to complete the two treatment series with oral VOR 400 mg doses combined with HXTC infusions over a 3 month period. VOR will be administered every 72 hours and each treatment series will consist of 10 doses of VOR 400 mg.

In Step 4 (Series 1), participants will receive two HXTC infusions along with 10 doses of VOR 400 mg. The HXTC infusions will be administered 6 hours after the 1st and 6th VOR doses.

In Step 5 (Series 2), participants will receive three infusions along with 10 doses of VOR 400 mg. The first two infusions will be administered 6 hours after the 11th and 16th doses of VOR. The 5th and final HXTC infusion will occur 1 – 3 days after the 20th VOR dose.

The 2nd and final leukapheresis will occur at least 4 weeks after the last HXTC infusion.

Resting cell infection frequency will be determined pre VOR-HXTC dosing with the baseline leukapheresis and post VOR-HXTC dosing with 2nd leukapheresis.

Longitudinal follow-up to measure the effectiveness of the intervention will continue for 9 weeks after the last HXTc infusion. Serial blood draws will be obtained pre and post-VOR-HXTc dosing throughout the study to monitor immune response.

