### **10.2. Outcome Measures**

#### **10.2.1. Primary Endpoints**

##### **10.2.1.1. Safety**

Occurrence of at least one  $\geq$  Grade 3 adverse event including signs/symptoms, lab toxicities, and/or clinical events that is possibly or definitely related to VOR or HXTc any time from the first day of study treatment through Step 6, Visit 23.

Safety data will include local and systemic signs and symptoms, laboratory measures of safety/toxicity, and all adverse and serious adverse events. Safety data will be routinely collected throughout the duration of the study.

NOTE: The occurrence of a Grade 3 infusion reaction that is sustained for less than 48 hours will not be included as a primary safety endpoint.

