**Table 5: Confidence Intervals for Depletion of the Latent Reservoir**

The SMC will receive monthly study progress and safety monitoring reports. Study feasibility and the achievement of study milestones will be assessed in these reports. Additionally, accrual, baseline characteristics, conduct of the study (including premature study discontinuations), any interruptions of ART, virologic failures, and all reported toxicities and events will be monitored during the study and sent to and discussed with the protocol team on a regular monthly basis. The study protocol team will review the individual safety data monthly to assess relation of all reported toxicities and AEs to the study treatment. The monthly data will be shared with the SMC for review.

It will be the responsibility of the study protocol team to interpret the toxicity data, make decisions needed to protect participants from undue risk, and determine whether or not participant replacements are needed.

If at any time during the study, two or more participants experience a toxicity that is Grade 3 or higher and definitely, probably, or possibly related to study treatment (as judged by the protocol team), then enrollment into the study will be temporarily suspended and the independent SMC will be asked to review all safety data; review the relation to study treatment of the event(s); and recommend how the study should proceed with respect to resuming enrollment and continuing study treatment.

Site monitors, independently contracted by the UNC HIV Cure Center, per contract with NIH/NHLBI will visit the clinical research site to review participants' records, including consent forms, CRFs, medical records (e.g., physicians' progress notes, nurses' notes, individuals' hospital charts), and laboratory records to ensure protection of study participants, compliance with the EC/IRB approved protocol/amendments, and accuracy and completeness of records. The monitors will inspect sites' regulatory files to ensure that local regulatory requirements, in addition to U.S. Federal regulations, are being followed. They will also inspect sites' pharmacies to review product storage and management.

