Review medical history (including new medical conditions)	X	X					X	X		X	X	X	
Assess Adverse Event	X	X					X	X		X	X	X	
Review ART & ART Adherence	X	X					X	X		X	X	X	
Review Concomitant Medication	X	X					X	X		X	X	X	
Phone Assessment	(T)		(T)	(T)	(T)	(T)	(T)		(T)	(T)	(T)	(T)	
Vorinostat Administration (400 mg) (home)	X		X	X	X	X	X		X	X	X	X	
CTL Infusion	X						X					X	
CTL Pre-medication	X						X					X	
Post infusion assessment	X	X					X					X	
Leukapheresis (& meal)													
Clinical Laboratory Procedures													
Chemistries		X 					X 				X 		
Coagulations (PT/INR/PTT)													
CBC with differential		X					X 			X			
Pregnancy Test or FSH Test													
CD4+ T Cell Differential Panel													
HIV-1 RNA PCR													
HBsAg & HCV Ab													
Donor ID Panel 													
RPR													
Urine Pregnancy – POCT 	X 						X 				X 		
Urinalysis													
Research Laboratory Procedures 													
Single Copy Assay		X											
PBMC - HDAC Responsive Gene Measurement	X	X					X 	X		X	X	X	
Single PK sample (VOR)							X						
Cells for CTL production													
HLA typing													
Immune Response, Viral Inhibition & Epitope Mapping													
Resting Cell Assay and CTL latency													

Step 6; Immune Monitoring						
Evaluations	IM Visit #1	IM Visit #2 Eliminated	IM Visit #3 & Leukapheresis #2	IM Visit #4	IM Visit #5 Eliminated	IM Visit #6 Eliminated
Time to Visit	~ 7 days after Visit 19		~ 4 weeks after Visit 19	~ 9 weeks after Visit 19		
Visit Windows	3 days (+/-)		1 week (+/-)	1 weeks (+/-)		
Study Week	13		16	21		
Study Visit	21	22	23	24	25	26
Clinical Procedures						
Consent, Eligibility, Demographics & Medical History						
Assignment of PID						
Assignment of SID						
Complete Physical Examination (vital signs & weight)			X			
Height						
Assess venous access						
Advancement Criteria						
Pre-Dose Clinical Assessment						
Targeted Clinical Assessment 	X			X		
Review medical history (including new medical conditions)	X		X	X		
Assess Adverse Event	X		X	X		
Review ART & ART Adherence	X		X	X		
Review Concomitant Medication	X		X	X		
Phone Assessment						
Vorinostat Administration (400 mg) (clinic)						
CTL Infusion						
CTL Pre-medication						
Post infusion assessment						
Leukapheresis (& meal)			X			
Clinical Laboratory Procedures						

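### The primary safety endpoint closes at Visit 23, 7 to 14 days short of the six-week post-infusion period in section 6.1.7, and sections 10.5 and 10.7.1 use a later end

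*Combined protocol and SAP*

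**What the plan says.** The documents give several different ends or timings that bear on the same endpoint.

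- **Endpoint (10.2.1.1).** A related Grade 3 or higher event counts if it occurs "any time from the first day of study treatment through Step 6, Visit 23".
- **Infusion-safety period (6.1.7).** "A period of six weeks following the completion of the last infusion will constitute the time required for clinical safety monitoring", and the same sentence extends this to reporting of infusion-related adverse events.
- **Timing of Visit 23.** Appendix A: about "4 weeks after Visit 19" (the last infusion), with a window of 1 week either side. Section 4.6: "approximately 5 weeks after the last HXTC infusion". Section 10.1, for the second leukapheresis, which is done at Visit 23: "at least 4 weeks after the last HXTC infusion".
- **Primary analysis (10.7.1).** For the safety endpoint, treatment-related events are to be described up to the end of study. Section 7.3.5.3 makes Visit 24 the end of study, and Appendix A places it about 9 weeks after Visit 19, plus or minus 1 week.
- **Suspension trigger (10.5).** "If at any time during the study, two or more participants experience a toxicity that is Grade 3 or higher", and the event is judged related, enrolment is suspended and the safety committee reviews the data.
- **Collection (9.2.3).** Adverse event reporting "lasts through the 30 days following the EOS visit in Step 6, Visit 24".

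**The concern.** The protocol names a period after the last infusion during which infusion-related harm must be watched for. It then closes the primary safety count before that period ends. A related Grade 3 event in week 6 would count toward suspension under section 10.5 and be described under section 10.7.1, yet that participant would score as event-free in the primary endpoint.

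With 12 participants, one event visibly changes the reported result. Because sections 10.2.1.1 and 10.7.1 give different ends for the same endpoint, two analysts could report different primary safety results from the same data and each cite the plan.

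**Working it through.** **1. The plan's own intervals.** Exact two-sided 95% limits (Clopper-Pearson), n = 12:

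- 0 events: the upper limit solves (1 − p)^12 = 0.025, so p = 1 − 0.025^(1/12) = 0.2646. Section 10.3 prints 0.26.
- 1 event: lower limit 0.0021 and upper limit 0.3848, from beta quantiles. Section 10.3 prints 0.00 and 0.38.

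The one-sided limits in section 10.4 also reproduce. For 0/12 they are 22.1% (95%) and 12.6% (80%); for 1/12 they are 33.9% and 23.0%. No printed figure is wrong. The question is which events enter the numerator.

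**2. Where Visit 23 falls for a completer.** Days are counted from Visit 19. The period in section 6.1.7 ends on day 6 × 7 = 42.

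| Source | Visit 23 day | Days of 42 uncovered |
|---|---|---|
| Appendix A, nominal | 28 | 14 (33%) |
| Appendix A, window edges | 21 to 35 | 21 to 7 (50% to 17%) |
| 10.1 lower bound with Appendix A late edge | 28 to 35 | 14 to 7 (33% to 17%) |
| 4.6, nominal | 35 | 7 (17%) |
| 4.6 with 1 week added | 42 | 0 |

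The row that respects both section 10.1 and Appendix A gives a gap of 7 to 14 days. The gap closes only if the Appendix A window is added to the figure in section 4.6, which neither place says to do.

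**3. Cross-check with the study weeks.** Visit 14 is Week 8 (day 56 of the treatment calendar). Visit 18 is 27 days later (day 83), and Visit 19 is 1 to 3 days after that (day 84 to 86). Week 16 is day 112, so Visit 23 falls 112 − 86 = 26 to 112 − 84 = 28 days after the last infusion. The week numbers therefore agree with about 4 weeks rather than with section 4.6.

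**4. Visit 24.** 63 ± 7 gives day 56 to 70, wholly after day 42 for a completer.

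**5. What one late event does.** It moves 0/12 (upper limit 0.26) to 1/12 (0.38). If one event has already been counted, it moves 1/12 to 2/12 (0.02 to 0.48). That exceeds the criterion of no more than 1 in 12 in section 10.4, if the criterion is applied to this endpoint.

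**6. How likely that is.** The documents give no rate for this gap. As an assumption only, a per-participant probability of 1% to 5% gives a chance of at least one such event among 12 of 1 − 0.99^12 = 11% to 1 − 0.95^12 = 46%.

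**The case against.** The best defence is that nothing is lost. Section 10.7.1 describes events to the end of study, section 10.5 has no Visit 23 cutoff, the section 10.4 criterion states no end date, and reporting runs 30 days past Visit 24. The monitoring duty in section 6.1.7 is therefore met in practice; that section sets a monitoring period and does not define an endpoint. All of this stands. It limits the problem to the binary count and its interval.

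Visit 23 is also a defensible close on laboratory grounds. It is the last visit with a full chemistry panel and a complete physical examination, whereas Appendix A marks a CBC but no chemistries at Visit 24. This too stands, as a cost of extending the window.

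A reader might infer more than the documents support:

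- **That the safety rate is biased downward.** A proportion defined to Visit 23 estimates risk to Visit 23. The window is shorter than section 6.1.7 implies, which is a mismatch of definition and not a biased estimate.
- **That half the six-week period is missed.** This needs Visit 23 on day 21, which the four-week minimum in section 10.1 excludes.
- **That unequal follow-up distorts the count of 12.** Sections 5.4 and 9.3 allow Visit 23 up to 8 weeks out for early discontinuers, but section 10.4 replaces participants who do not receive full treatment. The documents do not say whether those replaced stay in the safety denominator, so an effect cannot be shown.
- **That naming Visit 24 alone secures six weeks for everyone.** Visit 24 is timed from Visit 19, and no interval after Visit 23 is given for early discontinuers.

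**Conclusion.** The inconsistency holds and is of moderate weight. The primary endpoint ends 7 to 14 days before the protocol's own 42-day infusion-safety period for a completer, or up to 21 days if the Schedule's early edge is used without section 10.1. It also ends earlier than the analysis in section 10.7.1 and the trigger in section 10.5.

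A related Grade 3 or higher event in the gap would be recorded, described and open to safety committee review, but left out of the primary count and the section 10.3 interval. The consequence is a sensitivity to single events (0.26 against 0.38 for the upper limit), not a demonstrated error. The conclusion assumes that Visit 19 is the last study product and that the Appendix A and section 10.1 timings govern; under section 4.6 with a week added, the gap disappears. This is a should-fix, best settled before the safety data are analysed.

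**What to change.** In section 10.2.1.1, replace the end at Visit 23 with: through Step 6, Visit 24, and no less than 42 days after the last dose of either study product, applied in the same way to participants who stop early. Make section 10.7.1 refer to that same period. Reconcile the Visit 23 timings in sections 4.6 and 10.1 and Appendix A.

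For completers this needs no new visit or test, because Visit 24 already includes an adverse event assessment. For early discontinuers, Visit 23 falls at least 28 days after the last treatment and reporting continues for 30 days after Visit 24, so the reporting period extends past 28 + 30 = 58 days. However, section 9.2.9 does not require active enquiry after the final visit, so the 42-day floor should be stated explicitly.

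There are two costs. The reported safety rate may be slightly less favourable if a late event occurs. Laboratory detection after Visit 23 rests on what is already scheduled at Visit 24 (CBC, no chemistries), and the report should say so.

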##### **10.2.1.2. Change in the frequency of HIV infection per million resting CD4+T cells (RCI) from baseline to post-VOR/HXTc**

#### **10.2.2. Secondary Endpoints**

##### **10.2.2.1. The ability of combination VOR and HXTc therapy to increase HIV-1 specific immune responses in participants maintained on suppressive ART**

### **10.3. Sample Size Considerations**

For n=12 participants, if there are no primary adverse events (AEs), then the exact 95% confidence interval (CI) for the true AE rate will be [0.00, 0.26]. Thus, if no AEs are observed, one can confidently rule out event rates greater than 26%. If there is one AE among the 12 participants, then the exact 95% CI will be [0.00, 0.38].

#### 10.4. Safety

Since the trial will be stopped if two participants experience a study treatment-related toxicity of Grade 3 or higher, the criterion for safety of this study is grade 3 or 4 toxicity in no more than 1 of 12 participants. If 0 of 12 participants experience toxicity, we will have 95% confidence that the true toxicity rate is 22% or less and 80% confidence that it is 13% or less, based on 1-sided exact binomial confidence limits. If 1 participant has toxicity, the corresponding 95% and 80% 1-sided upper confidence limits are 34% and 23%, respectively.

Any participant who is not administered the full study treatment through Step 6 will be replaced until the target enrollment of participants is met.

Because a focus of the study is on safety and potential adverse events, accrual will be staggered such that enrollment and treatment administration will include a maximum of 2 participants per week, and never more than 1 on any day.

#### 10.5. Monitoring

Formal review will be performed at yearly intervals during the conduct of this study, and will be reviewed by an independent Safety Monitoring Committee (SMC). This review will be based on assessment of participant safety, and will serve as a basis for allowing enrollment to continue.

Observed proportion with >6 fold change from baseline	Exact 95% confidence interval
6/12=0.50	[0.21, 0.79]
7/12=0.58	[0.28, 0.85]
8/12=0.67	[0.35, 0.90]
9/12=0.75	[0.43, 0.95]
10/12=0.83	[0.52, 0.98]
11/12=0.92	[0.62, 1.00]
12/12=1.00	[0.74, 1.00]

**Table 5: Confidence Intervals for Depletion of the Latent Reservoir**

The SMC will receive monthly study progress and safety monitoring reports. Study feasibility and the achievement of study milestones will be assessed in these reports. Additionally, accrual, baseline characteristics, conduct of the study (including premature study discontinuations), any interruptions of ART, virologic failures, and all reported toxicities and events will be monitored during the study and sent to and discussed with the protocol team on a regular monthly basis. The study protocol team will review the individual safety data monthly to assess relation of all reported toxicities and AEs to the study treatment. The monthly data will be shared with the SMC for review.

It will be the responsibility of the study protocol team to interpret the toxicity data, make decisions needed to protect participants from undue risk, and determine whether or not participant replacements are needed.

If at any time during the study, two or more participants experience a toxicity that is Grade 3 or higher and definitely, probably, or possibly related to study treatment (as judged by the protocol team), then enrollment into the study will be temporarily suspended and the independent SMC will be asked to review all safety data; review the relation to study treatment of the event(s); and recommend how the study should proceed with respect to resuming enrollment and continuing study treatment.

Site monitors, independently contracted by the UNC HIV Cure Center, per contract with NIH/NHLBI will visit the clinical research site to review participants' records, including consent forms, CRFs, medical records (e.g., physicians' progress notes, nurses' notes, individuals' hospital charts), and laboratory records to ensure protection of study participants, compliance with the EC/IRB approved protocol/amendments, and accuracy and completeness of records. The monitors will inspect sites' regulatory files to ensure that local regulatory requirements, in addition to U.S. Federal regulations, are being followed. They will also inspect sites' pharmacies to review product storage and management.

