#### **6.2.3. Dosage, Preparation, and Administration of VOR**

The UNC IDS Pharmacy stores, distributes, and maintains accountability for VOR. The dispensing of each dose will be participant specific and by signed prescription. Upon receipt of the VOR doses from IDS, the study coordinator dispenses VOR to the participant in the research clinic according to the dose, schedule, and supportive care guidelines.

Take each VOR dose with food.

The primary IDS pharmacist will be responsible to the principal investigator for maintaining study drug accountability, reconciliation, and record maintenance during the study, including documentation of the amount of study treatments (VOR) received in IDS and the amount administered to each participant.

Participants will be provided their first dose of VOR 400 mg in Step 3, Visit 6 to take 4 in Step 4, Visit 7. Participants will take this dose at home in the morning prior to coming for Visit 7. The study coordinator will provide participants with individualized dosing instructions, clearly identifying the days they are required to take VOR. The study coordinator will contact participants on each dosing day. Participants will be instructed to contact the study coordinator and be prepared to return to the clinic should any adverse event evolve. Participants will be monitored for the development of toxicities. Participants will take the doses approximately 72 hours apart.

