## **7. STUDY SCHEDULE**

### **7.1. Study Procedures**

Participant study screening, eligibility, enrollment, baseline leukapheresis, and IUPM measurement are all completed and assessed during Step 1.

Study eligibility is determined at screening. Enrollment (Visit 2) occurs prior to or at the baseline leukapheresis procedure (leuk#1).

Enrolled participants advance to Step 3 if the baseline IUPM measurement is  $\geq 0.3$ .

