#### **7.3.3. Step 4 (Visits 7 – 13) - First Series of VOR 400 mg x 10 doses and 2 HXTC infusions**

## Visit Windows for Step 4

Visit #	Visit Evaluations	Visit Window
Visit 7	VOR Dose 1 and HXTC Infusion #1	≤ 21 days after Visit 6
Visit 8	Safety check and Research Labs	1 - 3 days after Visit 7
	VOR Dose #2	3 days after Visit 7 (Dose 1 + 3 days)
Visit 9	VOR Dose #3	6 days after Visit 7 (Dose 1 + 6 days)
	VOR Dose #4	3 days after Visit 9 (Dose 1 + 9 days)
	VOR Dose #5	6 days after Visit 9 (Dose 1 + 12 days)
Visit 10	VOR Dose #6 and HXTC Infusion #2	9 days after Visit 9 (Dose 1 + 15 days)
Visit 11	Safety Check and Research Lab	1 - 3 days after Visit 10
	VOR Dose #7	3 days after Visit 10 (Dose 1 + 18 days)
	VOR Dose #8	6 days after Visit 10 (Dose 1 + 21 days)
	VOR Dose #9	9 days after Visit 10 (Dose 1 + 24 days)
Visit 12	VOR Dose #10	12 days after Visit 10 (Dose 1 + 27 days)
Visit 13	Safety F/U & Step 5 Pre-Dose Clinical Assessment	7-14 days after Visit 12

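### After two related Grade 3 or higher toxicities, Section 10.4 stops the trial but Section 10.5 suspends only enrollment, so an enrolled, undosed participant may start treatment during the SMC review

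*Combined protocol and SAP*

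**What the plan says.** Section 10.4 (Safety) opens: "Since the trial will be stopped if two participants experience a study treatment-related toxicity of Grade 3 or higher". From that it derives a criterion: "the criterion for safety of this study is grade 3 or 4 toxicity in no more than 1 of 12 participants".

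Section 10.5 (Monitoring, in the text after Table 5) takes two or more participants with a Grade 3 or higher toxicity that is definitely, probably or possibly related. The action is: "then enrollment into the study will be temporarily suspended and the independent SMC will be asked to review all safety data". The SMC is then to "recommend how the study should proceed with respect to resuming enrollment and continuing study treatment". Nothing is said about dosing between the trigger and that recommendation.

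The protocol separates enrollment from treatment. Section 7.1: "Enrollment (Visit 2) occurs prior to or at the baseline leukapheresis procedure (leuk#1". The Step 4 visit table in Section 7.3.3 puts "VOR Dose 1 and HXTC Infusion #1" at Visit 7. Section 6.2.3 says of the first VOR capsules, which are handed out at Visit 6: "Participants will take this dose at home in the morning prior to coming for Visit 7".

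**The concern.** Two related Grade 3 or higher toxicities is the point at which the plan itself calls for safety to be reassessed. A reader of 10.4 would expect all activity to cease. A reader of 10.5 would stop enrolling and could carry on with those already in the study. The two instructions differ most for a participant who has been enrolled, whose product is being made or is ready, and who has not yet been exposed. That person has the most to gain from waiting for the SMC and the least to lose.

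The context adds some weight. Section 2.1 (Dose Rationale) raises the HXTC dose from 2 x 10^7 to as much as 1 x 10^8 cells/m², a fivefold increase, and Section 2.4 says participants gain no direct medical benefit.

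**Working it through.** **1. The plan's own figures.** The one-sided exact upper limits in 10.4 are the Beta quantile (c; x+1, 12−x).
- 0 of 12: 22.1% (95%) and 12.6% (80%). The plan gives 22% and 13%.
- 1 of 12: 33.9% and 23.0%. The plan gives 34% and 23%.

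Both reproduce. The dispute is about the rule, not these numbers.

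**2. Are the triggers the same?** Section 10.4 has two participants, treatment-related, Grade 3 or higher. Section 10.5 has two or more, the same grade, and spells out the relatedness categories. The second event sets off both.

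**3. Does suspending enrollment cover first dosing?** Sections 7.1 and 7.3.1 define enrollment as Visit 2. The stagger rule in 10.4 names enrollment and then, as a separate item, dosing: "treatment administration will include a maximum of 2 participants per week, and never more than 1 on any day". The suspension sentence in 10.5 names only enrollment.

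**4. Does another rule require a hold?**
- Sections 5.5.1, 9.1.2 and 9.1.3 end treatment for the participant who had the event.
- Sections 9.1.4.2 and 9.1.5 hold product only until the protocol team is consulted, not until the SMC reports.
- The PI review before an infusion (Section 7.3.3.1.2) concerns that participant's own labs and assessments. At Visit 7 it comes after the VOR dose taken at home.
- Section 5.4 lets the PI or team stop the study, and 10.5 obliges the team to protect participants. Both permit a hold; neither ties one to the trigger.

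**5. How long is the undosed interval?** Windows come from Appendix A and Section 7.3.2.2: leukapheresis to Visit 5, 4–6 weeks; Visit 5 to Visit 6, 4–10 weeks; Visit 6 to Visit 7, at most 3 weeks.
- Shortest: 4 + 4 + 0 = 8 weeks.
- Longest: 6 + 10 + 3 = 19 weeks.

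It is shorter for participants with a prior qualifying IUPM (Section 4.1) or stored HXTC (Section 4.3).

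**6. How many people?** Planned accrual is 12 participants in 36 months, or 156.5 weeks.
- Pace excluding the two triggering participants: 10 / 156.5 = 0.0639 per week. With all 12: 12 / 156.5 = 0.0767 per week.
- Enrolled, undosed and bound for dosing: 0.0639 × 8 = 0.51 to 0.0639 × 19 = 1.21.
- First dosings in a 2-week review: 0.0639 × 2 = 0.13 to 0.0767 × 2 = 0.15.
- First dosings in a 4-week review: 0.0639 × 4 = 0.26 to 0.0767 × 4 = 0.31.
- Visit 7 to Visit 19: 27 + (28 to 35) + 27 + (1 to 3) = 83 to 92 days, or 11.9 to 13.1 weeks. Times 0.0639, that is 0.76 to 0.84 participants in mid-series.

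The protocol gives no review length; 2 to 4 weeks is an assumption. The pace counts planned completers, so enrollees who fail the IUPM threshold or manufacturing are left out; they would not be dosed. The stagger rule's ceiling of two participants a week is far above the average pace.

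**The case against.** **The two sections can be reconciled.** The stop in 10.4 sits in a clause that introduces a precision statement and may be shorthand for the pause in 10.5. Section 10 also uses enrollment loosely: its 12 enrolled participants are those who complete, so suspending enrollment might be meant to include the undosed. This is a possible reading, but it is not written, and 10.5 pairs resumption with enrollment and continuation with treatment, which fits equally well with dosing going on during the review.

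**The team is not powerless.** It hears of related Grade 3 or 4 events within 24 hours, and the hold in 9.1.5 is not expressly limited to the affected participant. This stands. It shows that a hold can be imposed, not that the trigger imposes one. The separate monitoring plans cited in 12.3.3 and 12.4 were not available and may contain a halt procedure, but they would not remove the disagreement between 10.4 and 10.5.

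**Stronger readings that the documents do not support.**
- A reader might infer that the 1-of-12 criterion breaks down if the SMC lets the trial resume. It does not: at 2 of 12 it is simply not met, and the same exact method gives upper limits of 43.8% (95%) and 32.4% (80%).
- A reader might infer that dosing in Steps 4 and 5 must also be held. That is a trade-off: a pause of more than one week exceeds the HXTC delay the protocol permits and breaks the 72-hour VOR schedule.
- A reader might put the chance of the trigger at 12%, 34% or 73% (two or more of 12 at assumed true rates of 5%, 10% or 20%). That treats all 12 as still to be treated. Section 2.1 reports no treatment-related events by December 2019, with two more participants due under Version 2 and six under Version 3. If the earlier participants count toward the 12, at most 8 remained from that date, and the figures become 6%, 19% and 50%. The plan states no expected rate.

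**Conclusion.** The inconsistency is real and in current text. On one trigger, 10.4 stops the trial and 10.5 suspends only Visit 2 activity. Taken literally, the operative rule allows a first exposure at Visit 7 before the SMC has advised; preventing it depends on the team's discretion.

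The expected effect is small: about 0.13 to 0.31 first dosings per review, conditional on the trigger having fired, at the planned average pace and with an assumed 2 to 4 week review. The case for change rests on the safety rule giving two different instructions, not on that count. The finding does not extend to the safety criterion, and it does not determine what should happen to participants in mid-series.

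**What to change.** In Section 10.5, replace the enrollment-only suspension with:

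> *Enrollment and all first dosing (no advancement to Visit 7: no first VOR dose, including one already dispensed at Visit 6, and no first HXTC infusion) are suspended until the SMC makes its recommendation.*

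In Section 10.4, put the same wording in place of the statement that the trial stops. The coordinator's existing contact on each dosing day (Section 6.2.3) can be used to tell a participant not to take a dose already at home.

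The sponsor and SMC should also state one rule for participants already in Steps 4 and 5: hold or continue. A hold limits further exposure, but if it lasts more than a week it may cost a mid-series participant (0.76 to 0.84 expected at the trigger) their dosing windows or require a replacement. Continuing preserves the schedule but doses people while the safety question is open. The choice is theirs, but it should be written down beforehand.

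The cost is a few sentences, plus delay for undosed participants and repeat pre-dose labs if the 21-day window between Visits 6 and 7 lapses. The product is cryopreserved, so it can wait.
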